10.2. Efficacy Analyses

10.2.1. Primary Efficacy Endpoint Analyses

The primary endpoints of the study include ORR by IRC assessment in CTC-HRD-positive patients with measurable disease and PSA response rate in CTC-HRD-positive patients with or without measurable disease per PCWG3 criteria.

ORR is defined as the proportion of patients with best objective response of CR or PR confirmed at a subsequent timepoint ≥ 4 weeks later by IRC assessment. Patients without tumor assessment are considered non-responders.

ORR is assumed as 35% for pamiparib and estimated as 15% for historical control in the study population. The null and alternative hypotheses are set as follows:

$$H_0: \text{ORR} = 15\%$$

$$H_a: \text{ORR} > 15\%$$

PSA response rate is defined as the proportion of patients with PSA decline $\geq 50\%$ from baseline (confirmed by a second PSA value ≥ 3 weeks later).

PSA response rate is assumed as 50% for pamiparib and estimated as 30% for historical control in the study population. The null and alternative hypotheses are set as follows:

$$H_0 : \text{ORR} = 30\%$$

$$H_a : \text{ORR} > 30\%$$

Binomial exact tests will be performed for above hypotheses in the Efficacy-Evaluable Analysis Set. Two-sided binomial exact 95% CI of response rate will be constructed to assess the precision of the estimates.

To control the overall study type-I error rate, ORR and PSA response rate will be tested sequentially. If the ORR test shows significance at 1-sided 0.025 significance level, PSA response rate will be tested at a 1-sided 0.025 significance level.

The primary efficacy analyses will be conducted when mature response data have been observed, which will be determined by the sponsor.

A sensitivity analysis of response rate will be conducted using the Safety Analysis Set.

ORR and PSA response rate will be summarized in the specified subgroups: age group (< 65 versus ≥ 65), race, geographic region, ECOG performance status, BRCA1/2-mutant status, and number of prior lines of therapy.

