10.1. Analysis Sets

- Safety Analysis Set: includes all patients enrolled into the study who receive any dose of pamiparib. The Safety Analysis Set will be used for all safety analyses.
- Efficacy-Evaluable Analysis Set (ORR Assessment in Cohort 1 of [Table 2](#)): includes all patients in the Safety Analysis Set who had measurable disease at baseline and at least 1 postbaseline tumor assessment, unless they permanently discontinue pamiparib or the study early due to clinical progression or death before tumor assessment. The Efficacy-Evaluable Analysis Set is the primary analysis set for tumor response analysis.
- PSA-Evaluable Analysis Set (PSA Response Rate Assessment in Cohorts 1 and 2 of [Table 2](#)): includes all patients in the Safety Analysis Set as per Inclusion Criterion 7 at baseline (≥ 3 rising

PSA levels with ≥ 1 week between determinations and screening PSA ≥ 2 $\mu\text{g/L}$) and who had at least 1 postbaseline PSA measurement, unless they permanently discontinue pamiparib or the study early due to clinical progression or death before completed PSA assessment.

- PK Analysis Set: includes all patients who received pamiparib and for whom valid pamiparib PK parameters can be estimated.

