10.6. Sample Size Consideration

This study is designed to provide adequate power for primary endpoints of ORR and PSA response rate. A sample size of approximately 100 patients is planned (at approximately 45 centers with a projected average enrollment of 2 to 3 patients per center).

Assuming ORR of 35% for pamiparib in CTC-HRD-positive patients versus 15% for historical control in patients with measurable disease, the study power is 88% using a binomial exact test and 1-sided type-I error of 0.025 with $n = 50$. The binomial exact 95% CI of 35% ORR is 22.1% to 49.8% with a sample size of 50 patients.

Assuming PSA response rate of 50% for pamiparib versus 30% for historical control in CTC-HRD-positive patients with or without measurable disease, a sample size of 80 patients in this population will provide 95% study power using a binomial exact test and 1-sided type-I error of 0.025. The binomial exact 95% CI of 50% response rate is 38.6% to 61.4% with $n = 80$.

To explore the efficacy of pamiparib in patients with CTC-HRD-negative, but BRCA1/2-mutant mCRPC with or without measurable disease, approximately 20 patients will be enrolled in these cohorts.

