**Table 2 Primary and Secondary Efficacy Endpoint Analysis Populations**

	Efficacy Endpoint	Analysis Population
Primary	ORR by IRC	Efficacy-Evaluable Analysis Set (ORR Assessment in Cohort 1)
	PSA Response	Efficacy-Evaluable Analysis Set (PSA Response Rate Assessment in Cohorts 1 and 2)
Secondary	DOR by IRC	Efficacy-Evaluable Analysis Set (ORR Assessment in Cohort 1), those w/objective response per IRC
	ORR by INV	Efficacy-Evaluable Analysis Set (ORR Assessment in Cohort 1)
	Time to Objective Response by INV	Efficacy-Evaluable Analysis Set (ORR Assessment in Cohort 1), those w/confirmed objective response per INV
	Clinical Benefit Rate by INV	Efficacy-Evaluable Analysis Set (ORR Assessment in Cohort 1)
	Time to PSA Response	Efficacy-Evaluable Analysis Set (PSA Response Rate Assessment in Cohorts 1 and 2), those w/confirmed PSA response
	Duration of PSA Response	Efficacy-Evaluable Analysis Set (PSA Response Rate Assessment in Cohorts 1 and 2), those w/confirmed PSA response
	Time to PSA Progression	Safety Analysis Set (Cohorts 1 and 2)
	Time to SSE	Safety Analysis Set (Cohorts 1 and 2)
	rPFS by IRC	Safety Analysis Set (Cohorts 1 and 2)
OS	Safety Analysis Set (Cohorts 1 and 2)	

Abbreviations: DOR = duration of response; INV = investigator; IRC = independent review committee; ORR = objective response rate; OS = overall survival; PSA = prostate-specific antigen; rPFS = radiographic progression-free survival; SSE = symptomatic skeletal event.

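### Protocol 10.2.1 and the synopsis name the ORR analysis set for the PSA primary test and label its hypotheses ORR, contradicting the PSA population, the n = 80 and the SAP

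*Protocol*

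**What the plan says.** Protocol 10.2.1 defines the second primary endpoint as "PSA response rate in CTC-HRD-positive patients with or without measurable disease per PCWG3 criteria". It then sets out two pairs of hypotheses. The first is ORR against 15%. The second follows the PSA definition and uses the 30% PSA historical rate, but its symbols still read ORR = 30% and ORR > 30%. One sentence gives the test population for both: "Binomial exact tests will be performed for above hypotheses in the Efficacy-Evaluable Analysis Set". The tests run in sequence, and if ORR is significant, "PSA response rate will be tested at a 1-sided 0.025 significance level". The synopsis repeats the block, including the mislabelled hypotheses.

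Protocol 10.1 labels the Efficacy-Evaluable set as the one for ORR in Cohort 1, limits it to treated patients "who had measurable disease at baseline and at least 1 postbaseline tumor assessment", and makes it primary for tumor response. Patients who stop early for clinical progression or death before a scan are kept. The same section defines a PSA-Evaluable set for PSA response in Cohorts 1 and 2, with no measurable-disease condition. Section 10.2.1 never names it.

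Protocol 10.6 bases the PSA power on all of Cohorts 1 and 2: "a sample size of 80 patients in this population will provide 95% study power using a binomial exact test".

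SAP 6.1 has two sets that share the name Efficacy-Evaluable, one for ORR and one for PSA. SAP Table 2 and SAP 6.4.1 assign the primary PSA analysis to the second, "Efficacy-Evaluable Analysis Set (PSA Response Rate Assessment in Cohorts 1 and 2"). SAP 6.4.1 also writes the hypotheses in terms of PSA response rate.

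**The concern.** The population of a primary hypothesis test should be stated once, without contradiction. Here the protocol's operative sentence points both tests at a set whose definition admits only patients with measurable disease. Cohort 2 is bone only and is planned at about 30 of the 80 patients in the PSA endpoint. Applied as written, the sentence would remove all of them from a test meant to cover patients with or without measurable disease, and the sample-size statement would no longer describe that test.

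The hypothesis labels add to this. Read literally, the block gives ORR two different null values and gives PSA response none. The set name also means different things in the two documents: in the protocol, Efficacy-Evaluable is one ORR set; in the SAP it covers two sets, one of them for PSA. Anyone programming from the protocol alone, or reusing its text in a later study, could take the wrong population.

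**Working it through.** **Inputs**
- Null and alternative PSA rates of 30% and 50%: "Assuming PSA response rate of 50% for pamiparib versus 30% for historical control" (Protocol 10.6).
- One-sided 0.025, exact binomial (Protocol 10.2.1 and 10.6).
- Cohort 1 planned at 50 and Cohort 2 at 30 (Protocol 3.1). Together 50 + 30 = 80.

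**Formula.** With X binomial(n, p), the critical count r is the smallest k for which P(X ≥ k | n, 0.30) ≤ 0.025. Power is P(X ≥ r | n, 0.50).

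**Step 1: the plan's own figure, n = 80.**
P(X ≥ 32 | 80, 0.30) = 0.0360, too large. P(X ≥ 33 | 80, 0.30) = 0.0211, so r = 33. Power = P(X ≥ 33 | 80, 0.50) = 0.9535, or 95.4%. The stated 95% is reproduced. The stated interval also reproduces: the Clopper-Pearson 95% limits for 40/80 are 38.6% and 61.4%.

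**Step 2: the protocol sentence taken literally, Cohort 1 only, n = 50.**
P(X ≥ 22 | 50, 0.30) = 0.02509, which just misses 0.025. P(X ≥ 23 | 50, 0.30) = 0.0123, so r = 23. Power = P(X ≥ 23 | 50, 0.50) = 0.7601, or 76.0%. The difference from Step 1 is 95.4 − 76.0 = 19.4 points.

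**Step 3: sensitivity to the evaluable count.** Cohort 1 is only approximately 50, and exact power is saw-toothed in n.

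| n | r | exact alpha | power |
|---|---|---|---|
| 45 | 21 | 0.0135 | 72.4% |
| 46 | 21 | 0.0180 | 76.9% |
| 47 | 21 | 0.0235 | 80.9% |
| 48 | 22 | 0.0148 | 76.5% |
| 49 | 22 | 0.0195 | 80.4% |
| 50 | 23 | 0.0123 | 76.0% |
| 51 | 23 | 0.0161 | 79.9% |
| 52 | 23 | 0.0209 | 83.4% |

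Over this range the literal reading gives about 72% to 83%, which is about 12 to 23 points below 95.4%.

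**Step 4: the PSA sets compared.** The protocol's PSA-Evaluable set and the SAP's PSA version of the Efficacy-Evaluable set have the same content: treated patients in Cohorts 1 and 2, Inclusion Criterion 7 met at baseline, at least one later PSA value, and the same exception for early clinical progression or death. Only the name differs.

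**The case against.** The best defence is that the documents, read together, leave little doubt about the intended analysis. The label of the PSA-Evaluable set in Protocol 10.1 ties it to PSA response in Cohorts 1 and 2. The same section confines the primary role of the Efficacy-Evaluable set to tumor response. The endpoint definition and the n = 80 both include bone-only patients. Section 10 of the protocol leaves analysis details to the SAP, and the SAP puts the PSA test in Cohorts 1 and 2. The ORR = 30% label follows directly on a sentence about the PSA historical rate, so it reads as a slip. All of this stands as evidence of intent.

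It also rules out two stronger readings that a reader might infer. The first is that bone-only patients drop out of the PSA test and its power falls to about 76%. The documents do not support this: the SAP analysis keeps Cohort 2, and 76.0% belongs only to a literal reading with exactly 50 evaluable patients. The second is that protocol and SAP specify substantively different PSA populations. They do not: the SAP applies the criteria of the protocol's PSA-Evaluable set under another name.

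The defence does not make the protocol sentence correct. A test population is more than a detail; the protocol states it in two places, and both are inconsistent with its own set definitions. SAP section 8, on changes to the planned analysis, does not mention the difference.

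**Conclusion.** The point holds as a contradiction in the protocol's primary test population and hypothesis labels. Section 10.2.1 and the synopsis name a set that cannot contain Cohort 2, against the PSA endpoint definition, the PSA-Evaluable set, the n = 80 and the SAP. The most likely explanation is a drafting error, not a design choice.

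The power figures are conditional. They assume true rates of 30% and 50%, concern the PSA test alone, and ignore the requirement that ORR be significant first. The 95.4% also assumes that all 80 patients are evaluable.

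The practical effect on this trial is nil. SAP section 8 records termination after 13 patients, no efficacy analysis, and PSA data in listings only. What remains is the accuracy of the record and the risk if the text is reused.

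**What to change.** In Protocol 10.2.1 and the synopsis:
- Write the PSA hypotheses as H0: PSA response rate = 30%; Ha: PSA response rate > 30%.
- Replace the single sentence on the test population with two assignments: ORR tested in the Efficacy-Evaluable Set (Cohort 1), and PSA response tested in the PSA-Evaluable Set (Cohorts 1 and 2).

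In the SAP:
- Use the protocol's name, PSA-Evaluable, for the PSA set in section 6.1, Table 2 and the PSA endpoint text, so that each name means one set in both documents.
- Note the correction in section 8.

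The cost is wording only. The SAP already carries the intended populations and hypotheses, so the sample size, the test and the reported results are unchanged.

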10.2.2. Secondary Efficacy Endpoint Analyses

DOR by IRC assessment, ORR by investigator, and time to objective response and clinical benefit rate as assessed by investigator will be evaluated in patients with CTC-HRD-positive mCRPC with measurable disease per PCWG3 criteria.

Time to PSA response, duration of PSA response, time to PSA progression, time to SSE, rPFS by IRC, and OS will be evaluated in patients with CTC-HRD-positive mCRPC with or without measurable disease per PCWG3 criteria.

DOR is defined as the time from the date of the earliest documented confirmed response of CR or PR to radiographic disease progression by IRC or death due to any cause, whichever occurs first.

Time to objective response is defined as the time from the date of the first dose of study drug to the first documented confirmed response of CR or PR.

Clinical benefit rate is defined as the proportion of patients with a documented confirmed response of CR, PR, or stable disease.

Time to PSA response is defined as the time from the date of the first dose of study drug to the first documented confirmed PSA response.

Duration of PSA response is defined as the time from the date of the earliest documented confirmed PSA response to PSA progression or death due to any cause, whichever occurs first.

Time to PSA progression is defined as the time from the date of the first dose of study drug to a $\geq 25\%$ increase in PSA with an absolute increase of ≥ 2 $\mu\text{g/L}$ above the nadir (or above the baseline for patients with no PSA decline after 12 weeks), confirmed by a second value ≥ 3 weeks later.

Time to SSE is defined as the time from the date of the first dose of study drug to the first symptomatic fracture, radiation or surgery to bone, or spinal cord compression.

rPFS is defined as the time from the date of the first dose of study drug to radiographic disease progression by IRC or death due to any cause, whichever occurs first.

rPFS censoring rule will follow US Food and Drug Administration Guidance for Industry, Clinical Trial Endpoints for Approval of Cancer Drugs and Biologics ([FDA 2007](#)). Data for patients without PD or death at the time of analysis will be censored at the date of the last tumor assessment. Data for patients who initiated new anticancer therapy will be censored at the last tumor assessment date before the introduction of new anticancer therapy. Data for patients who had 2 or more consecutive missed scheduled tumor assessments immediately before PD will be censored at the last tumor assessment date before the 2 missed tumor assessments. Further details will be described in the Statistical Analysis Plan.

OS is defined as the time from the date of the first dose of study drug to death due to any cause.

Time-to-event variables of DOR, duration of PSA response, time to PSA progression, time to SSE, rPFS, and OS will be estimated using the Kaplan-Meier method. The median of these time-to-event variables will be presented along with their 2-sided 95% CI using the Brookmeyer and Crowley method (Brookmeyer and Crowley 1982).

Descriptive statistics will be provided for time to objective response and time to PSA response. Only responders will be included in analyses for DOR, duration of PSA response, time to response, and time to PSA response.

The ORR as assessed by investigator and its exact 2-sided 95% CI will be reported.

[figure not shown]
10.3. Pharmacokinetic Analyses

Pamiparib concentrations will be summarized by nominal time of collection. Descriptive statistics will include means, medians, ranges, and standard deviations, as appropriate.

Population PK analysis may be carried out to include plasma concentrations from this study in an existing model. Additional PK parameters such as apparent clearance (CL/F) of the drug from plasma and area under the plasma concentration-time curve from 0 to 12 hours postdose (AUC₀₋₁₂) may be derived from the population PK analysis if supported by data.

Exposure-response (efficacy or safety endpoints) analysis may be carried out if supported by data. The results of the population PK and exposure-response analyses may be reported separately from the clinical study report.

10.4. Exploratory Analyses

10.5. Safety Analyses

Safety will be assessed by monitoring and recording of all AEs. Laboratory values, vital signs, physical examinations, and ECG findings will also be used in determining the safety of the study treatment.

10.5.1. Extent of Exposure

Extent of exposure to pamiparib will be summarized descriptively as the duration of exposure (days), cumulative total dose received per patient (mg), dose intensity (mg/day), and relative dose intensity.

The number (percentage) of patients requiring dose reductions, pamiparib holds, and permanent pamiparib discontinuation due to AEs will be summarized. Frequency of dose reductions and pamiparib withholding will be summarized by categories.

10.5.2. Adverse Events

The AE will be coded using Medical Dictionary for Regulatory Activities Version 20.0 or higher and graded using NCI-CTCAE Version 4.03 or higher.

A TEAE is defined as an AE that had an onset date on or after first dose of pamiparib or was worsening in severity from baseline (pretreatment) up to 30 days following permanent discontinuation of pamiparib or initiation of new anticancer therapy, whichever occurs first. All TEAEs will be included in summary tables and in-patient data listings.

The incidence of TEAEs will be reported as the number (percentage) of patients with TEAEs by system organ class and preferred term. A patient will be counted only once by the highest grade according to NCI-CTCAE Version 4.03 or higher within a system organ class and preferred term, even if the patient experienced more than one TEAE within a specific system organ class and preferred term. The number (percentage) of patients with TEAEs will also be summarized by relationship to the study treatment. Treatment-related AEs include those events considered by the investigator to be related to study treatment or with missing assessment of the causal relationship. SAEs, deaths, TEAEs \geq Grade 3, pamiparib-related TEAEs, and TEAEs that led to pamiparib withholding or permanent discontinuation will also be summarized.

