1.5.2.1. Pharmacokinetics Data for BGB-290-AU-002

1.5.2.2. Exploratory Biomarker Data

1.5.2.3. Clinical Safety and Preliminary Efficacy for BGB-290-AU-002

BGB-290-AU-002 is a Phase 1a/1b study to evaluate the safety, PK, food effect, and antitumor activity of pamiparib in patients with advanced solid tumors. The Phase 1A portion is a first-in-human study evaluating pamiparib to characterize the safety, the maximum tolerated dose, preliminary antitumor activity, and the PK of pamiparib given as a monotherapy in a 3+3 dose escalation scheme. In Phase 1a Part 1, pamiparib was administered in doses ranging from 2.5 to 120 mg orally twice a day.

The study is being conducted in Australia. Preliminary data for 45 patients in the Phase 1a Part 1 portion of the study are available (cutoff date of 01 December 2017) and are presented below unless noted otherwise.

The preliminary safety data indicate that the most frequent nonhematologic adverse events (AEs) ($\geq 10\%$ of patients) were nausea (64%, n = 29), vomiting (36%, n = 16), fatigue (33%, n = 15), diarrhea (29%, n = 13), abdominal pain (22%, n = 10), constipation, urinary tract infection (each 18%, n = 8), upper respiratory tract infection (16%, n = 7), ascites, pyrexia, headache, and decreased appetite (each 11%, n = 5).

Hematologic AEs are of interest in this study. Anemia was most frequent (33%, n = 15), followed by neutropenia (11%, n = 5) and platelet count decreased (4%, n = 2).

Twenty-seven (60%) patients experienced \geq Grade 3 AEs (regardless of relatedness). Ten (22%) patients experienced \geq Grade 3 AEs that were considered related to pamiparib by the investigator: anemia (13%, n = 6), neutropenia (7%, n = 3), nausea, fatigue, diarrhea, oral paresthesia, paresthesia, and hypophosphatemia (each 2%, n = 1).

Serious AEs (SAEs) were reported in 25 (56%) patients, and for 3 (7%) patients they were considered related to pamiparib by the investigator: anemia (4%; n = 2) and nausea (2%; n = 1). Three (7%) patients discontinued study drug because of an AE: vomiting, paresthesia of the hands and mouth, and traumatic hematoma (due to a fall) (each n = 1).

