9.1.5. Laboratory Test Abnormalities

Abnormal laboratory findings (eg, chemistry, hematology, or coagulation) or other abnormal assessments (eg, ECGs, x-rays, or vital signs) that are judged by the investigator as clinically significant will be recorded as AEs or SAEs. This includes clinically significant abnormal laboratory findings or other abnormal assessments that are present at baseline and significantly worsen during the study. The definition of clinically significant is entrusted to the judgment of the investigator. In general, these are the abnormalities that:

- Are associated with clinical signs or symptoms, or

- Require active medical intervention, or
- Lead to dose interruption or discontinuation, or
- Require close observation, more frequent follow-up assessments, or
- Further diagnostic investigation

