### 6.5.2 Adverse Events

AEs will be graded by the investigators using CTCAE v4.03. The AE verbatim descriptions (investigator terms from the CRF) will be classified into standardized medical terminology using the Medical Dictionary for Regulatory Activities (MedDRA) Version 20.0 or higher.

A treatment emergent adverse event (TEAE) is defined as an AE that had an onset (including worsening from pretreatment) date on or after the first dose of study treatment through 30 days after the last dose of study treatment or initiation of new anti-cancer therapy, whichever occurs first. Only TEAEs will be included in summary tables. All AEs, treatment emergent or otherwise, will be presented in patient data listings.

An overview table, including the number and percentage of patients with TEAEs, serious TEAEs, grade 3 or higher TEAEs, treatment-related TEAEs, TEAEs that led to death, and TEAEs that led to treatment discontinuation, dose reduction or dose interruption will be provided. Treatment-related TEAEs include those events considered by the investigator to be related to study treatment or with missing assessment of the causal relationship.

The incidence of TEAEs will be reported as the number and percentage of patients with TEAEs by SOC and PT. A patient will be counted only once by the highest severity grade within an SOC and PT, even if the patient experienced more than 1 TEAE within a specific SOC and PT. The number and percentage of patients will be summarized by SOC and/or PT for the following:

- TEAEs

- Treatment Related Grade 3 or higher TEAEs
- Serious TEAEs
- TEAEs that led to treatment discontinuation
- TEAEs that led to dose modification

TEAEs will also be summarized by PT in descending order. A listing of all AEs and AEs that led to treatment discontinuation will be provided.

All deaths and causes of death will be provided in a listing, including those occurring during the study treatment period and those reported during the survival follow-up period after treatment completion/discontinuation.

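### Adverse events are tabulated by single preferred term only, so a cytopenia's AE count can be divided between rows; a prespecified grouped-term table is a cheap improvement

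*Protocol*

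**What the plan says.** Protocol 10.5.2 sets the rule for TEAEs: "The incidence of TEAEs will be reported as the number (percentage) of patients with TEAEs by system organ class and preferred term". SAP 6.5.2 repeats it: "The incidence of TEAEs will be reported as the number and percentage of patients with TEAEs by SOC and PT". The counting unit is the patient: "A patient will be counted only once by the highest severity grade within an SOC and PT". The SAP applies the same by-term layout to related Grade 3 or higher events, serious events, and events leading to discontinuation or dose modification. Its ranked table also uses single terms: "TEAEs will also be summarized by PT in descending order".

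Neither document names a grouped term, a standardized query or a list of events of special interest for hematologic toxicity. Yet the Phase 1 background in Protocol 1.5.2.3 states: "Hematologic AEs are of interest in this study".

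Protocol 9.1.5 says that abnormal laboratory findings "that are judged by the investigator as clinically significant will be recorded as AEs or SAEs". It prescribes no reporting term.

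After early termination, SAP Section 8 drops the efficacy tables but keeps the safety analyses as planned, so the rule still applies.

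**The concern.** A low hemoglobin that an investigator judges clinically significant can be written as anemia at one site and as hemoglobin decreased at another. The same holds for neutrophils and platelets. These are different preferred terms, and the tables count within a term. Patients with one toxicity could then appear in two rows. Neither row would be its incidence, and the rows could not be added if some patients carry both terms.

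The opportunity for mixed wording exists. Protocol 10.6 plans about 45 centers with 2 to 3 patients each, and SAP 6.5.2 codes from investigators' own terms. The Phase 1 summary uses both styles across toxicities: "Anemia was most frequent (33%, n = 15), followed by neutropenia (11%, n = 5) and platelet count decreased (4%, n = 2".

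At stake is how clearly the report shows toxicities that the plan itself treats as important. In Phase 1, anemia and neutropenia led the related events of Grade 3 or higher. Anemia, neutropenia and thrombocytopenia each have their own entries in the Protocol 6.1.4 dose-modification table (Table 4).

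**Working it through.** **1. The plan's own figures.** Protocol 1.5.2.3, N = 45, any grade: anemia 15/45 = 33.3%, neutropenia 5/45 = 11.1%, platelet count decreased 2/45 = 4.4%. These match the stated 33%, 11% and 4%. For context, nausea was 29/45 = 64.4%, related Grade 3 or higher anemia 6/45 = 13.3%, and related Grade 3 or higher neutropenia 3/45 = 6.7%.

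**2. What splitting can do to one row.** Let *a* be the patients with the disorder term, *b* those with the laboratory term, *o* those with both, and *G* those with either, among *N* treated.

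- G = a + b − o, so max(a, b) ≤ G ≤ min(a + b, N).
- Also max(a, b) ≥ (a + b)/2 ≥ G/2. The larger row therefore never shows less than half of the grouped count, and it shows all of it when only one term is used.

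**3. Illustration.** The documents give neither the split nor the overlap. Assume a grouped anemia rate equal to the Phase 1 rate, no patient with both terms (o = 0), and a laboratory-term share of 0%, 25% or 50%. Counts are rounded to whole patients.

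| Share under laboratory term | N = 100, G = 33: rows | Larger row | N = 13, G = 4: rows | Larger row |
|---|---|---|---|---|
| 0% | 33 and 0 | 33% | 4 and 0 | 4/13 = 30.8% |
| 25% | 25 and 8 | 25% | 3 and 1 | 3/13 = 23.1% |
| 50% | 16 and 17 | 17% | 2 and 2 | 2/13 = 15.4% |

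Overlap makes adding rows unsafe. If 26 patients carry one term, 12 the other and 5 both, then G = 26 + 12 − 5 = 33. The larger row gives 26 and the sum gives 38.

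**4. What other planned outputs already cover.**

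| Quantity for a cytopenia | Where reported | Affected by AE wording? |
|---|---|---|
| Frequency and worst grade of the laboratory value | Protocol 10.5.3; SAP 6.5.3 grade summaries and shift tables; SAP Table 4 lists hemoglobin, platelets, white cells, neutrophils and lymphocytes | No |
| Patients with any serious, related, Grade 3 or higher or fatal TEAE, or one leading to discontinuation, reduction or interruption | SAP 6.5.2 overview table | No, but not specific to a toxicity |
| Patients with reductions, holds or discontinuation due to AEs | Protocol 10.5.1 | No, but not specific to a toxicity |
| Patients with that cytopenia as an AE, by relatedness, seriousness and dose action | SAP 6.5.2, by SOC and/or single term only | Yes |

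The gap is the last line.

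**The case against.** The strongest reply is that no split is documented. The Phase 1 summary gives one term per toxicity. Its style differs between toxicities, not within one. Protocol 9.1.5 says when a laboratory abnormality becomes an AE, not how it is worded, and Protocol 8.1 leaves entry to eCRF completion guidelines that are not in these documents and may settle the wording. That the two kinds of term fall under different system organ classes is a dictionary convention, not stated here. All of this stands, and the effect may be zero.

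Second, the laboratory tables already show how often each count fell and how far. This stands for frequency and worst grade. It does not extend to relatedness, seriousness or dose action. Those breakdowns are planned, although the secondary safety endpoint names only incidence, timing and severity.

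Third, at 13 patients the AE listings can be pooled by eye. That is true, but the terms to pool would then be chosen after the data are seen.

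A reader might go further and infer that each hematologic toxicity is split and that the drug's main toxicity is understated. The documents support neither statement. Nausea (64%) was more frequent than anemia (33%), and the Phase 1 dose-limiting toxicities in Protocol 1.5.2.3 were not hematologic. Nor would a Grade 2 and a Grade 3 entry become two events: the tables count patients, so that patient would appear once in each row.

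**Conclusion.** The point holds as an inexpensive improvement, not as an error in the planned tables. Because counting is by single term and no grouped hematologic term is prespecified, the AE incidence of a cytopenia by relatedness, seriousness and dose action can be understated. The larger row may fall short of the grouped count by anything from nothing to about half. This rests on an assumption that the documents neither confirm nor exclude: that sites use both kinds of term for the same toxicity. The percentages in the table above are illustrations on assumed shares.

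Any understatement is confined to the by-term AE tables. The laboratory grade and shift tables, the overview table and the counts of dose changes due to AEs are unaffected. One patient in 13 is 7.7 percentage points, so a split would be visible in a table, but the listings make it easy to detect and the practical weight is small.

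**What to change.** Add to SAP 6.5.2, with a matching line in Protocol 10.5.2, a prespecified list of grouped terms:

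- anemia with hemoglobin decreased;
- neutropenia with neutrophil count decreased;
- thrombocytopenia with platelet count decreased;
- optionally, leukopenia with white blood cell count decreased (it has no entry of its own in the Protocol 6.1.4 dose-modification table, so the case for it is weaker).

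Count each patient once per group at the worst grade. Show one table with columns for all-cause, related, Grade 3 or higher, serious, and leading to hold, reduction or discontinuation. Keep the existing SOC and preferred-term tables beside it, and fix the list before the tables are run.

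The cost is a short term list and one extra table from data already collected. Hematologic AE rates may look slightly less favourable. No study procedure or treatment rule changes.
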